#### **IIIC.4f.3. Variables to Determine Eligibility or Supplementary/Exploratory Variables in Hypothesis Testing**

**IIIC.4f.3a. Demographic Information:** Caregivers will report their education level, yearly income, per capita income, employment status, duration of unemployment in the past 2 years, hours worked per week, numbers and ages of children and adults in the household, and relations of all household members to one another.

**IIIC.4f.3b. Psychiatric Diagnostic Screen:** The Kiddie Schedule for Affective Disorders and Schizophrenia – Present and Lifetime Version (K-SADS-PL), a semi-structured interview, will be administered separately to the parent and youth to screen for present and lifetime history of psychiatric illness.

**IIIC.4f.3b. Behavioral/Emotional Problems:** The Child Behavior Check-List (CBCL) is an instrument designed for parents to rate the child's problem behaviors (120 items) as well as competencies (20 items) in the past 6 months. Youth rate the same items using the Youth Self-Report (YSR).

**IIIC.4f.3c. Reward-drive Traits:** The Behavioral Inhibition System and the Behavioral Activation System (BIS/BAS) is a 24-item self-report scale that assesses motivational systems. The BIS is sensitive to the signals of punishment and non-reward, whereas the BAS taps into appetitive motivation and is sensitive to the signals of reward. The BAS correlated positively with the high-risk choice on the WOF task. We will assess whether BAS score modulates neural and cognitive-emotional self-regulation changes in response to the PAAS intervention.

**IIIC.4f.3d. Risky Behaviors:** This construct consists of alcohol/drug use and sexual behavior, each with three separate constructs (willingness, intention, and actual behavior). Intention and willingness will be measured in addition to behaviors as the participants are young and will have limited opportunity to engage in risky behaviors within the short follow-up period despite manifesting some risky behaviors. Prior longitudinal research has shown that intention and willingness are good predictors of alcohol/drug use and sexual risk behavior (IIIC.3b).

*Behavior Willingness* is assessed by asking participants to imagine themselves in different situations and then to think about how they might respond if they were in that situation (**Appendix 1**). Opportunities for access to risky situations and prototype peers also are assessed. It includes 32 items for alcohol/drug use and 23 items for sexual behavior. *Behavior Intention* is measured with four items on alcohol/drug use, and four items on sexual behavior. *Behavior Engagement* consists of three items for alcohol/drug use (two concerning lifetime behavior and one concerning recent use) and three items to assess age of onset of sexual activity and unprotected sex.

**IIIC.4f.3e. Regulated, Communicative Parenting:** This index consists of three measures (**Appendix 1**).

**IIIC.4f.3e.1. Involved-vigilant Parenting:** The scale is composed of 19 items, rated on a 5-point Likert scale, that assesses parental involvement, inductive discipline, consistent discipline and monitoring.

**IIIC.4f.3e.2. Communication about Risky Behaviors:** Articulated norms and expectations regarding risky behaviors consists of two scales. The first is a 6-item scale that assesses parents' communication of expectations regarding the use of alcohol and other substances on a 5-point Likert scale. Another scale modified for communication patterns about sexual issues assesses whether parents ever talked to the child about topics such as reproduction/having babies, menstruation, sexually transmitted diseases and HIV/AIDS.

**IIIC.4f.3e.3. Adaptive Racial Socialization:** The Racial Socialization Scale includes 15 items rated on a 3-point Likert scale to assess whether parents transmit explicit messages to youth about strong work orientation, race relations, and coping with racism and discrimination in the workplace, educational institutions and community.

**IIIC.4f.3f. MRI Safety Screen:** Screening for metallic objects/devices and claustrophobic symptoms will be done with a standardized instrument utilized by VUIIS.

**IIIC.4f.3g. Handedness:** Handedness will be verified using the modified version of the Edinburgh Handedness Test, with right-handedness defined by a score >20 out of possible 28.

**IIIC.4f.3h. Physical/Laboratory Measures:** Participants will rate their pubertal status based on the illustrations of stages of pubertal development. Blood will be drawn for serum gonadal steroids (estradiol, progesterone and testosterone). In exploratory analyses, we will examine the effect of pubertal stage and gonadal hormones on neural responses, as there likely will be a greater variation in pubertal maturation at this age range (11-13 years). A urine test will provide qualitative and quantitative information on substance use (amphetamines, benzodiazepines, cannabinoids, cocaine, ethanol, opiates, oxycodone, and phencyclidine). Sexually active females will have a urine test to rule out pregnancy for the MRI studies.

**IIIC.4f.4. Data Collection Protocol:** Trained staff members will conduct the assessments. They will have a minimum of 40 hours of training and supervised practice on how to obtain informed assent/consent, build rapport, interview, and assist participants on the computer-based data collection system and PAAS-technology program. Data collection will occur at clinical sites, the PI's lab, participants' homes or community settings, based on the participants' choices. Families will use the computer-based data system to complete assessments using audio computer-assisted self-interview (ACASI) procedures, which are integrated into the remote data management system (IIIC.7a). Each computer will have headphones, the computer screen will display one question at a time, and all information that appears on-screen also will be read to participants by the computer. Compared with face-to-face interviews and self-administered surveys, ACASI offers privacy and confidentiality that, in turn, elicits less social desirability bias, and more accurate reports on questions about sensitive issues or negative behaviors. The use of ACASI in our previous studies reduced missing data, increased consistency and eliminated literacy requirements. Psychiatric diagnostic interviews will be conducted by trained research assistants. [name] was involved in the development and testing of the K-SADS-PL. Prior to initiating the study, reliability will be assessed (requiring  $\geq 85\%$  agreement). In order to avoid reliability drift over time, reliability checks will be made annually. All interviews will be audio-taped, and a random selection of 15% of the interviews will be co-rated by [name].

**IIIC.4f.5. Randomization:** A 2 (gender) x 2 (Tanner stage) x 2 (intervention) randomized, matched-pairs, block-design will be used to stratify participants based on gender and Tanner stage (I-II, III-V) comprising 4 blocks for 128 participants. Within each block, 16 pre-randomized (PAAS or wait-list) pairs based on order of intake will be prepared in advance. Randomization will proceed as follows: the first youth to enter the study in each block will be assigned to either PAAS or wait-list (based on pre-randomization for that pair) and the second will be assigned to the opposite condition. The third youth will be assigned to either PAAS or wait-list (based on pre-randomization for that pair) and the fourth will be assigned to the opposite condition. The randomization based on the order of entry will continue in this manner until all matched pairs within each of the 4 blocks are filled.

**IIIC.4f.6. PAAS Protocol:** PAAS is a 6-week, technology-delivered, family-based youth risk intervention program (Table 2). PAAS uses a set of six (one per week) DVDs or the web to deliver separate sessions for parents and youth, and joint sessions in which they both engage on the same computer to integrate and practice the skills they have just learned in their separate sessions. Each weekly session takes about 45 minutes to complete, for an average of 90 minutes per participant (45 minutes separate plus 45 minutes joint), and a total of 9 hours for the 6-week intervention. Each session includes a review, a virtual discussion, and observing and interacting with four parent and four youth Avatars that reflect phenotypes of AAs, with voice-overs by AA parents and youth. Videos portraying family interactions and intrapersonal processes are integrated into each session to convey key points of the intervention along with interactive activities to promote skill-building and to reinforce learning. PAAS also includes a technology tutorial and an introductory session. After receiving detailed instructions face-to-face, the program will be accessible through a website to participants who prefer using the Internet, or it will be downloaded onto laptop computers and delivered to them at their homes or other locations convenient to the participants, such as participating clinics or community settings (e.g. churches, community centers).

The PAAS curriculum will likely influence the neural pathways by: 1) providing opportunities for youth to negotiate novel situations in a safe environment until they gain better adaptive skills in self-control; 2) fostering resistance-efficacy in high-risk situations, and reinforcing positive self-image and encouraging future orientation through goal-setting; and 3) encouraging youth to think about the potential consequences of risky behaviors from their parents' perspective (IIIC.3b; Table 2). Each of these pathways has evidence to suggest that reward-drive and cognitive-control/self-regulation neural circuits are involved. Parents play an important role in protecting youth against risky behaviors by providing warmth as well as consistent, inductive discipline.

Data from the computer/web, which tracks time spent on the computer and the completion of activities, will be downloaded to a secure server. Participants also will complete questions pertinent to each intervention session to ensure that they grasped the main concepts. The computer-based program was selected for the following reasons. Families can experience a computer intervention when it is most convenient for them and at their own pace. It can be accessed at home or another convenient site where a computer is available. Computer literacy and familiarity, even among those from economically-disadvantaged households, is nearly universal now. Our studies (IIIC.3b), as well as those of others, that included AA youth and adults have shown that computer-based prevention programs can be very engaging and motivating. The privacy that computer-based interventions afford is particularly important in close-knit, ethnic-minority communities, in which participants typically know one another outside the intervention context and privacy is a key concern.

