### III C. APPROACH

**IIIC.1 Overview:** The conceptual model guiding our study is presented in **Fig 1**. Aim 1 will assess the effects of PAAS on the magnitude of Phase 2 functional connectivity between reward-drive and cognitive-control neural circuitry at rest and during a decision-making task after controlling for pre-intervention (Phase 1) levels. Aim 2 will evaluate if Phase 2 post-treatment neural circuitry changes mediate PAAS' effects on psychological processes (i.e. cognitive and emotional self-regulation) at the 3-month follow-up (Phase 3) after controlling for Phase 1 values. Our overarching hypothesis is that the functional connectivity between reward and cognitive-control networks correlates with self-regulation, and that PAAS increases the magnitude of functional connectivity between these neural networks. In addition to these hypotheses, we will identify characteristics (demographic, neurobiological, psychological, behavioral and social-contextual factors) that moderate PAAS' effects on the relationship between functional brain changes and cognitive-emotional self-regulation in exploratory analyses (IIIC.3b; **Fig 2**).

A total of 128 AA volunteers (ages 11-13 years, 50% male and female) and 128 parents (primary caretakers) will be recruited. Youth and parents will complete assessments on intervention targets (i.e. parenting processes, youth psychological protective factors and cognitions/behaviors associated with HIV and SUD vulnerability). fMRI scans will be acquired in the youth to assess functional connectivity between reward-drive and cognitive-control neural circuitry during rest and while performing a decision-making task involving probabilistic monetary rewards. A second task that assesses general impulsivity/motor response inhibition (in contrast to reward-drive) will be included as a supplementary measure. Following assessments, the families will be randomized to either PAAS or a wait-list control condition for 6 weeks. fMRI scans will be repeated after 6 weeks to measure functional brain changes from pre-to-post intervention. They will repeat the intervention-targeted assessments 3 months later, after which the wait-list controls will be offered PAAS as a benefit for participation in the study (IIIC.4f.1; **Fig 6**).

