#### IIIC.4f. Methods

**IIIC.4f.1. Overview:** A description of the protocol/procedures is provided (IIIC.4f.2 - IIIC.4f.6; **Fig 6, Table 1**). Eleven-to-thirteen year-old AA youth and their parents will complete information on demographic and health status as part of their clinic visits. Families selected randomly from the eligible pool will be invited to participate, while at the clinic or later via mail (**IV.A.2a, Human Subjects**). Research is an integral part of these participating clinical programs and processes are in place for a smooth transition from clinical care to research that follows the Institutional Review Board and Health Insurance Portability and Accountability Act (HIPAA) guidelines. When contact is made, they will be provided information about the study, with an overview of the time commitment and assessments. Interested families will be screened further to determine eligibility by obtaining medical, psychiatric and treatment history.

**Phase 1 (Pre-intervention Assessments):** Information on psychiatric symptoms, psychosocial factors and risky behaviors will be completed. Those who meet eligibility criteria will have a blood draw for gonadal hormones and receive training on the fMRI tasks and have a mock scan. A urine sample will be obtained to test for alcohol/drug use and pregnancy. They then will complete baseline fMRI studies. **Phase 2 (Intervention Phase):** The families will be randomized using procedures described in IIIC.4f.5 to PAAS or wait-list condition (1:1 ratio) for the 6-week intervention period. PAAS consists of 6 web- or DVD-based weekly sessions, 90 minutes per session; the first half includes individual, concurrent curricula for caregivers and youth, and the second half is a family-joint session designed for practicing the skills learned in the individual sessions. At the end of the 6-week intervention period, the urine drug test and fMRI studies will be repeated in both groups. **Phase 3 (Follow-up Phase):** Three months after the intervention phase, both psychosocial and risky-behavior assessments will be repeated. The wait-list group then will be offered the PAAS intervention as a benefit for participation in the study.

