				5-10 Days		Starts within 14 Days of Screen						
				1	2	3	4	5	6	7	8	
Visit	Parent	Youth	Minutes			Wk 1	Wk 2	Wk 3	Wk 4	Wk 5	Wk 6	
Intervention Week												
Clinic/Telephone Screen	X	X	15-30	X								
Informed Consent/Assent	X	X	45-60			X						
Demographic Information	X		10-20			X						
Psychiatric Diagnostic Screen	X	X	30-60			X						
Youth Beh/Emotional Problems	X	X	20-30			X						
Reward-drive Traits		X	15-20			X						
Risky Behaviors		X	15-20			X						
Resistance Efficacy		X	10-15			X						
Self-control		X	15-20			X						
Future Orientation		X	10-15			X						
Emotion Regulation		X	5-10			X						
Self-image		X	5-10			X						
Self-esteem		X	5-10			X						
Impulsivity		X	5-10			X						
Involved-vigilant Parenting	X	X	10-15			X						
Risk-behavior Communication	X	X	10-15			X						
Adaptive Racial Socialization	X	X	10-15			X						
MRI Safety Screen	X	X	5-10			X						
Handedness Scale		X	5-10			X						
Tanner Stages		X	5-10			X						
Serum Gonadal Steroids		X	10-15			X						
Urine Alcohol/Drug Test		X	10-15			X						
Urine Pregnancy Test		X	0			X						
Task Practice/Mock Scanner		X	60-90			X						
Resting and Task-based fMRI		X	90-120			X						
PAAS Intervention	X	X	90-100			X	X	X	X	X	X	

and most of the cerebellum (TR/TE = 2000/25 msec, FOV = 24 cm, matrix = 64 × 64). This sequence was designed to preserve the signal in the striatum and ventral PFC, areas which are susceptible to signal drop-out. An automated higher-order shim procedure will be applied to minimize potential magnetic field inhomogeneities.

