### IIIC.7. Statistical Methods

**IIIC.7a. Data Management:** Data management will be done via remote electronic data capture (*REDCap*). REDCAP was developed at VUMC to insure data integrity and completeness, including compliance with HIPAA (over 300,000 users). Data will be entered immediately after testing on data entry screens designed to duplicate the data collection forms (ACASI; **IIIC.4f.4**). Reports can be generated to track all contacts with the participants.

**IIIC.7b. Procedures for Handling Missing Data:** Missing data will be accounted for by including "missingness" as a covariate if the proportion of missing data is small, or alternatively using multiple imputation methods if the proportion of missing data is large, e.g. >5%.

**IIIC.7c. Data Reduction:** Each hypothesis will be examined using a primary variable, with supplemental information gained from analysis of other related measures (**see IIIC.5**).

**IIIC.7d. Data Analysis:** Descriptive statistics (e.g. means and standard deviations, frequencies and histograms) will be computed for all variables, along with 95% bootstrap confidence intervals. Significance tests will be two-tailed, with  $p < 0.05$ , controlling for multiple comparisons. Pubertal stage/gonadal hormones, gender and SES will be included as concomitant variables in analyses where they are known to correlate with the outcome. These covariates, while not of primary interest, will reduce residual variance and increase the precision of effect estimates for improved statistical power. Secondary analyses will determine if these covariates significantly affect the outcomes. Behavioral/emotional problem score (CBCL/YSR), lifetime history of substance use and dose of the intervention (number of completed sessions) will serve as additional potential covariates.

**IIIC.7d.1. Hypothesis 1:** PAAS will induce greater functional connectivity changes in the reward-drive and cognitive-control (fronto-striatal) circuitry compared to the wait-list condition. Post-treatment neural connectivity

scores will be regressed on group assignment (PAAS vs. wait-list) as the independent variable and baseline (pre-treatment) neural connectivity score as a covariate. Two separate models will be run for resting-state and task-based fMRI connectivity measures. Other covariates (IIIC.7d) will be included if there are group differences.

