### **IIIC.10. Potential Problems and Alternative Strategies**

**IIIC.10a. Recruitment and Retention Issues:** Recruitment and retention will be challenging. However, we are confident that we can manage these challenges because: (1) as previously described in **IIIC.4a**, we will have as our recruitment partners primary care and nonprofit service providers that see large numbers of youth and that [name] has successfully worked with on prior studies; and (2) we will employ retention procedures that we have used successfully with similar populations.

In previous studies, we have successfully recruited high-risk samples (low SES, mood and addictive disorders) and implemented intensive protocols (multi-dimensional clinical and biological measures with admissions for sleep/neuroendocrine studies lasting up to 3 consecutive days) that included much more lengthy longitudinal designs (follow-up assessments at 6-month intervals for up to 5 years). Also, [name] has more than 20 years of experience conducting community-based research, recruiting and retaining over 2,000 AA parents and youth in developmental and prevention studies. We had low attrition rates (10-20%) in these studies, and we will follow the same procedures, including evening/weekend appointments to accommodate participants, reminder calls the day before and on the appointment day, providing meals/snacks during visits, engaging local community partners and offering clinical and social service referrals to families when needed. We will provide reimbursement for travel and use a reimbursement protocol that is incentive-based (i.e. based on the number of visits attended). The PAAS intervention (tech version) also is feasible to implement at home at the participants' convenience.

**IIIC.10b. Inherent Confounds in the Study Design:** Even though invitations will be sent to randomly selected families, the participation will be based on their willingness and meeting subsequent stringent eligibility criteria. Hence, the findings might not generalize to the larger AA population. The participating clinics maintain electronic databases with demographic and clinical characteristics, and we will compare the sample with the remaining clinic population (and those who declined to participate or were excluded after the invitation) on these features. The other confounds related to restricted age range and race/ethnicity have been addressed (**IIIC.4d**, **IIIC.4e**).

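### Fixed pairs within four strata make 64 of the 128 assignments certain once the stratum and the first youth's arm are known; the likely bias is small and the remedy is cheap.

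*Combined protocol and SAP*

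**What the plan says.** Section IIIC.4f.5 stratifies by gender and Tanner stage (I-II against III-V), giving four strata. Each has 16 pairs prepared in advance and filled by order of intake. The first youth of a pair takes the listed arm and "the second will be assigned to the opposite condition". The same rule is repeated for every pair until the strata are full.

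Other sections bear on how far this can be exploited:

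- IIIC.4f.1: "Families selected randomly from the eligible pool will be invited to participate".
- IIIC.1: "Following assessments, the families will be randomized to either PAAS or a wait-list control condition for 6 weeks". Eligibility checks and the baseline scan therefore precede assignment.
- IIIC.7d.1: the Hypothesis 1 regression uses the "baseline (pre-treatment) neural connectivity score as a covariate".
- IIIC.10b: despite random invitation, "the participation will be based on their willingness and meeting subsequent stringent eligibility criteria".
- IIIC.4f.4: staff training covers "how to obtain informed assent/consent, build rapport, interview, and assist participants on the computer-based data collection system and PAAS-technology program". It does not say that one person screens, schedules and sees allocations.

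**The concern.** The comparison is PAAS against a wait-list, so a youth's arm is apparent soon after assignment. Under the pair rule, the first arm discloses the second. Concealing the list protects the first member of each pair only.

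If someone who influences entry knows the next arm, eligibility judgements, encouragement or the order of entry can make the arms differ. Adjusting for baseline connectivity removes the part of that difference carried by the measured baseline. It does not remove a difference in an unmeasured trait that also predicts the outcome, and such a difference would be read as an effect of PAAS.

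**Working it through.** **Count.** 4 strata x 16 pairs x 2 youths = 128, which reproduces the plan's total. Second members: 4 x 16 = 64, or 50%. Best-guess accuracy: (1/2)(1/2) + (1/2)(1) = 75%, or 96 of 128.

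**Inputs for bias.** IIIC.6 gives 102 analysed after 20% attrition, so 51 per arm. The standard error of the arm difference is sqrt(2/51) = 0.198 residual SD. Alpha is 0.05 two-sided (IIIC.7e). The documents give nothing for the next two inputs, so both are assumptions:

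- delta: the shift, in SD of an unmeasured trait, of youths whose arm is predictable;
- rho: the correlation of that trait with the baseline-adjusted outcome, taken as 0.2 to 0.5.

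**Formulas.** Half of each arm consists of second members. Steering the predictable slots of one arm (32 of its 64) gives bias = 0.5 x delta x rho. Steering both arms in opposite directions gives bias = delta x rho. False-positive rates come from the noncentral t distribution with 51 per arm.

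| Scenario with pairs | Bias (residual SD) | False-positive rate |
|---|---|---|
| One-way, delta 0.1 | 0.01 to 0.025 | 5.0% to 5.2% |
| One-way, delta 0.3, every predictable slot | 0.03 to 0.075 | 5.3% to 6.6% |
| Two-way, delta 0.3, every predictable slot | 0.06 to 0.15 | 6.0% to 11.7% |

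Simulation of the outcome regressed on arm and baseline (baseline correlation 0.3, 0.5 or 0.7; 6,000 runs per cell) agrees. At delta 0.3, one-way bias is 0.031 to 0.032 for rho 0.2 (rate 5.0%) and 0.075 to 0.078 for rho 0.5 (rate 6.6% to 6.9%). Steering wholly through the measured baseline leaves no bias after adjustment.

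**If the only lever is re-ordering two waiting youths of one stratum.** Assume 14 to 19 recruiting quarters (Table 3 is damaged in the text reviewed). At 13 weeks per quarter, 32 youths per stratum means one every 5.7 to 7.7 weeks. Table 1 carries the heading "Starts within 14 Days of Screen". The Poisson chance of another arrival within 14 days is 30% to 23%. With one-way delta 0.3, bias runs from 0.23 x 0.15 x 0.2 = 0.007 to 0.30 x 0.15 x 0.5 = 0.023, and the rate is 5.0% to 5.2%.

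**Effect of varying blocks of 4 and 6** (simulated lists totalling 32 per stratum):

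- Certain assignments fall from 50% to about 1% for an observer who tracks only the running imbalance, 5.6% for one who knows both sizes, and 10.1% for one who also knows the list make-up.
- Best-guess accuracy falls only from 75% to 69.4%.
- Two-way steering on the best guess shifts the trait by 4 x delta x (accuracy - 0.5). At delta 0.3 this is 0.30 SD with pairs and 0.233 SD with 4/6 blocks. On the outcome, 0.06 to 0.15 becomes 0.047 to 0.116 SD, and 6.0% to 11.7% becomes 5.6% to 9.0%.
- If staff see half of earlier assignments, certain slots are 25% with pairs against 0.3% with 4/6 blocks, and guessing is 63% against 59%. If they see none, the two lists are equally unpredictable.

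**The case against.** The count is conditional, and the plan narrows the conditions. Half of the stratum definition is Tanner stage, which the youth self-rates (IIIC.4f.3h) and which may not be known at invitation or consent. The diagnostic interview requires at least 85% agreement, is audio-taped, and 15% of interviews are co-rated (IIIC.4f.4). Nothing supplied says that recruiters see earlier allocations, and the text between IIIC.1 and IIIC.3 and the Human Subjects section cited in IIIC.4f.1 are not in the material reviewed; concealment may be described there. The steering sizes are assumed. The 14-day window may be too generous: if 5 to 10 of those days go on Phase 1, 4 to 9 remain and the re-ordering chance drops to about 7% to 20%. By the figures above, changing the blocks reduces guessing only modestly.

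Most of this is fair, and it limits the weight of the point without removing it. Tanner stage and the diagnostic checks belong to Phase 1, before randomisation, so the stratum can be known before assignment. Silence on concealment is not counted as a fault here; the point rests on the stated pair rule. The shorter window only lowers a side scenario. The modest fall in guessing is the reason to pair the new blocks with restricted sight of earlier assignments.

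**Conclusion.** The point holds as a cheap improvement that should be made; it is not evidence that the trial is biased. That 64 of 128 assignments are certain given the stratum and first arm is exact if all pairs fill.

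That the likely bias is small is a judgement resting on the assumed delta and rho. The one-way ceiling of 0.03 to 0.075 SD is 0.15 to 0.38 of a standard error. Stronger steering would matter: a 0.2 SD shift in the outcome itself on all 64 predictable slots, in opposite directions by arm, would raise the false-positive rate to about 17%. Under the formula above that needs, for example, delta 0.4 with rho 0.5. Nothing in the documents suggests steering of that kind, but nothing bounds it.

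The pairing also buys little: the Hypothesis 1 regression has no pair term, so its gain is tight balance alone.

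**What to change.** Keep the four strata and randomisation after baseline. Before enrolment:

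1. Replace the pairs with permuted blocks of randomly varying size, for example five blocks of 4 and two of 6 (20 + 12 = 32), or two of 4 and four of 6 (8 + 24 = 32), in random order in each stratum. Do not disclose the sizes or the list make-up.
2. Have someone outside recruitment hold the list and release each assignment only after eligibility and baseline data are locked.
3. Where feasible, keep earlier assignments from staff who screen and schedule. This may be incomplete in an unmasked trial, so it complements step 1.
4. Include gender and Tanner stratum in the analysis model unconditionally. IIIC.7d and IIIC.7d.1 now include them only where they are known to correlate with the outcome or if the groups differ.

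The cost is a new list and some separation of existing roles, with no extra participants, visits or scans. If recruitment stops before the strata fill, imbalance can reach 3 per stratum and 12 in total, against 1 and 4 with pairs. In 20,000 simulated trials with each stratum stopped at 20 to 31 youths, the mean absolute total imbalance was 1.6 against 1.1, and the 95th percentile 4 against 3. Adjusting for strata does not restore equal arm sizes.
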